8.3 Adverse Events and Serious Adverse Events

The definitions of an AE and a SAE are in [Appendix 3](#).

8.3.1 Time Period and Frequency for Collecting Adverse Event and Serious Adverse Event Information

The AE reporting period for safety surveillance begins upon endometrial transformation (Visit 2) and continues until the End of Study Visit.

Any SAE assessed as related to study intervention must be recorded and reported, as indicated in [Appendix 3](#), whenever it occurs, irrespective of the time elapsed since the last administration of study intervention.

The method of recording, evaluating, and assessing causality of AEs (including SAEs) and the procedures for completing and transmitting SAE reports are in [Appendix 3](#).

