9.4.1.3 Safety Endpoint(s)

Safety parameters will include the incidence and severity of all AEs.

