9.4.4 Safety Analyses

Safety Analyses will be performed using the Safety population.

Data on AEs will be collected on scheduled and unscheduled visits, based on information spontaneously provided by the participant and/or by questioning the participant. The most current version of Medical Dictionary for Regulatory Activities (MedDRA) and the World Health Organization Drug Dictionary (WHODRUG) coding dictionaries will be used for AEs, medical conditions, and concomitant medications. Number and percentage of patients with AEs or SAEs will be presented according to System Organ Class and the preferred term from the MedDRA dictionary.

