### 5 Objectives and Endpoints

Objectives	Endpoints (Outcome Measures)	Endpoints (Outcome Measures) Timeframe	IAP section
Primary			
To investigate the ongoing pregnancy rate of Crinone® compared to Crinone® in combination with Duphaston® during artificial FET cycles in Chinese population.	Ongoing pregnancy	At 10-12 weeks of pregnancy [8-10 weeks after ET]	14.1
Secondary			
To evaluate the efficacy of Crinone® compared to Crinone® in combination with Duphaston® for luteal phase support in artificial FET cycles.	

• β-hCG positive

	At 4 weeks of pregnancy [2 weeks after ET]	14.2
	

• Implantation

• Clinical pregnancy

	At 6-8 weeks of pregnancy [4-6 weeks after ET]	14.2

Objectives	Endpoints (Outcome Measures)	Endpoints (Outcome Measures) Timeframe	IAP section
To evaluate the safety of Crinone® compared to Crinone® in combination with Duphaston® for luteal phase support in artificial FET cycles.	• Early abortion	Time from ET to 12 weeks of pregnancy	14.2
	• Luteal phase bleeding	Time from ET to β-hCG positive assessment	15.2.3
	• Vaginal bleeding	Time after β-hCG positive assessment	15.2.3
	• The safety profile of the study intervention	Time from the first day of study intervention after randomization to last dose of study intervention date or the clinical cut-off date, whatever occurs earlier.	15

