#### Definitions

**Treatment-emergent adverse events (TEAEs):** those events with onset dates occurring within the treatment periods. The **treatment period** is defined from the first day of study intervention after randomization until last dose of study intervention date or the clinical cut-off date, whatever occurs earlier.

All analyses described in Section 15.1 will be based on TEAEs if not otherwise specified.

Adverse events **related to study intervention** are those events with relationship missing, unknown or yes.

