## 15.1.1 All Adverse Events

Unless otherwise stated, adverse events will be displayed in terms of frequency tables: by primary system organ class (SOC) in alphabetical order and preferred term (PT) in incidence descending order.

If an adverse event is reported for a given subject more than once during study intervention, the worst severity and the worst relationship to study intervention will be tabulated.

In addition, the following overall frequency table will be prepared by primary SOC in alphabetical order and PT in incidence descending order:

- Any TEAE
  - Any either trial drug related TEAEs
  - Any Crinone only related TEAEs
  - Any Duphaston only related TEAEs
  - Any TEAEs related to both drugs
- Any serious TEAEs
  - Any either trial drug related serious TEAEs
  - Any Crinone only related serious TEAEs
  - Any Duphaston only related serious TEAEs
  - Any serious TEAEs related to both drugs
- Any AE by worst severity
  - Any either trial drug related TEAEs by worst severity
  - Any Crinone only related TEAEs by worst severity
  - Any Duphaston only related TEAEs by worst severity
  - Any TEAEs related to both drugs by worst severity
- AEs leading to death (AEs with Grade 5 or outcome “fatal” if grade 5 not applicable)
  - Any either trial drug related TEAEs leading to death (AEs with Grade 5 or outcome “fatal” if grade 5 not applicable)
  - Any Crinone only related TEAEs leading to death (AEs with Grade 5 or outcome “fatal” if grade 5 not applicable)
  - Any Duphaston only related TEAEs leading to death (AEs with Grade 5 or outcome “fatal” if grade 5 not applicable)
  - Any TEAEs related to both drugs leading to death (AEs with Grade 5 or outcome “fatal” if grade 5 not applicable)

---

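### The SAP's AE and SAE tables stop at the last dose, while the protocol collects adverse events to the End of Study Visit and plans their tabulation without that limit

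*SAP*

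**What the plan says.** **SAP.** Section 15.1 (Definitions) starts the treatment period at the first dose after randomisation and runs it "until last dose of study intervention date or the clinical cut-off date, whatever occurs earlier". No days are added after the last dose. The default is then set: "All analyses described in Section 15.1 will be based on TEAEs if not otherwise specified". In 15.1.1 the SAE row reads "Any serious TEAEs", so it carries the limit in its own label. Two other rows in 15.1.1, on worst severity and on events leading to death, are headed AE and not TEAE, so their scope is ambiguous. The Section 5 objectives table gives the same timeframe for the safety profile ("after randomization to last dose of study intervention date or the clinical cut-off date, whatever occurs earlier"). Section 7 lists two changes from the protocol, the confidence interval method and the move of early abortion to efficacy. The AE window is not among them. Section 15.2.2 refers back to 15.1.1 and promises subject listings without saying whether late-onset SAEs are included.

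**Protocol.** Under 8.3.1 the AE reporting period "begins upon endometrial transformation (Visit 2) and continues until the End of Study Visit", and a related SAE must be recorded "whenever it occurs, irrespective of the time elapsed since the last administration of study intervention". Section 9.4.1.3 states: "Safety parameters will include the incidence and severity of all AEs". Section 9.4.4 plans the tables without an on-treatment restriction: "Number and percentage of patients with AEs or SAEs will be presented" by system organ class and preferred term. Appendix 3 makes spontaneous abortion and ectopic pregnancy SAEs by definition.

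**The concern.** The protocol's safety parameter is all AEs, and its planned counts have no cut at the last dose. The SAP's tables have one. An event that starts after a woman's last dose but before her End of Study Visit is collected and then left out of the AE tables. If it is serious, it is also left out of the SAE table.

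This matters here because pregnancy losses are SAEs by definition. A miscarriage dated after the last dose would appear in the early-abortion table but not in the SAE table, so two outputs of the same report would give different counts. Vaginal bleeding after the pregnancy test, which protocol 9.4.1.2 treats as an AE, could differ in the same way between SAP 15.2.3 and the AE tables. No SAP output names ectopic pregnancy. If one were dated after the last dose, its appearance as a safety event would depend on how 15.2.2 is read.

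**Working it through.** The plan gives no figure to reproduce. The check compares the two windows and then sizes one omission.

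**1. Which limit applies.** The SAP window ends at the last dose or the clinical cut-off, whichever comes first. SAP Section 6 holds the final analysis until the last subject has completed and the database is locked. The cut-off therefore does not shorten the window; the last dose does.

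**2. The two windows, from the first dose after randomisation.**
- Protocol 8.3.1: to the End of Study Visit, with no limit for related SAEs.
- SAP 15.1: to the last dose plus 0 days.

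**3. When they differ.** Under Appendix 4, drug continues to the ongoing pregnancy assessment, stops at a miscarriage, or ends with a negative pregnancy result, which triggers the End of Study procedures. For women who follow this course the gap is near zero. Two routes leave one:
- Rescue medicine (protocol 6.5.1) is a change of drug or of dose at threatened abortion, and these women may remain in the study. A change of dose leaves the window open. If study drug is replaced, the window closes while observation goes on.
- Protocol 4.1 foresees women who enter the study and later discontinue study intervention, and SAP 15.1.2 tabulates discontinuation of either drug.

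**4. Possible length of the gap.** The Schedule of Activities gives Visit 4 at Day 14 ± 1, Visit 5 at Day 35 ± 7 and Visit 6 at Day 63 ± 10.
- Drug stopped at Visit 4, next seen at Visit 5: 35 − 14 = 21 days nominal; at most 42 − 13 = 29.
- Drug stopped at Visit 5, next seen at Visit 6: 63 − 35 = 28 days nominal; at most 73 − 28 = 45.

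These are the spans the schedule allows for a woman who stays in the study off drug. They do not say how many women will be in that position.

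**5. Where an event with onset after the last dose would appear.**
- Miscarriage: in the early-abortion analysis (SAP 14.2, to end of study); not in the SAE table.
- Vaginal bleeding: in SAP 15.2.3 (to end of study); not in the TEAE tables.
- Death: in SAP 15.2.1, which covers all deaths.
- Ectopic pregnancy or another SAE: not in the SAE table; in the 15.2.2 listing only on the wider reading.
- Another non-serious AE: in no table, unless the ambiguous rows of 15.1.1 are read as covering all AEs.

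**6. Effect of one omission.** With 334 women (protocol 4.1) randomised 1:1 (6.3.1), each arm has 334 / 2 = 167. A woman whose only AE, or only SAE, starts after her last dose lowers that arm's percentage by 1 / 167 = 0.00599, or 0.6 percentage points. This takes every randomised woman to be in the safety population; with fewer, the effect per woman is slightly larger.

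**The case against.** The strongest reply is that the design leaves almost nothing to omit. Drug runs to the last scheduled visit or to the loss. Because it is stopped when a miscarriage occurs, the loss normally falls inside the window. Ectopic pregnancy is looked for at Visit 5, when a woman following the protocol is still on drug. Protocol 7.2 treats withdrawal from intervention and from study together and regards observation as complete once the cycle has failed. No off-drug visit schedule is described. Wholly missing onset dates are moved to the start of treatment or to the AE resolution date if that is earlier (SAP 15.1), which does not push events past the last dose. This stands, and it is why the expected number is small. It does not close the gap, because 6.5.1 allows women on rescue medicine to stay and 4.1 foresees early discontinuation.

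A second reply is that 8.3.1 governs collection, that the protocol's analysis section sets no window, and that the SAP was free to specify one. In part this stands: a TEAE window is a normal choice, and the Section 7 entry is only documentation. But 9.4.1.3 says all AEs and 9.4.4 has no on-treatment limit, so tables restricted to TEAEs alone deliver less than the protocol describes.

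A third reply is that 15.2.2 lies outside 15.1, so its listing may cover every SAE. That reading is open. The cross-reference to 15.1.1 leaves the narrower one open too.

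A reader might infer more than the documents support:
- *That the comparison between arms is biased.* Nothing shows that women come off drug early, or have late events, more often in one arm.
- *That late losses and deaths vanish from the report.* Miscarriages, bleeding and deaths have outputs without this cut. Clinical pregnancy as defined includes ectopic pregnancy, although that count does not identify it as a safety event.
- *That the SAP hides the narrowing.* The window is stated in Section 5 and again in 15.1.

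**Conclusion.** The point holds as a limited mismatch. By default the AE tables, and by its own label the SAE row, stop at the last dose with no added days, against a protocol that collects to the End of Study Visit and plans counts of AEs and SAEs without that limit. The events exposed are those in women who are off study drug but still in the study.

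Their number cannot be computed from the documents and is probably small or zero. Each woman omitted costs about 0.6 percentage points in one arm, assuming 167 per arm in the safety population. No effect on the comparison between arms is shown. The change is still worth making, because the omission follows from a stated rule, it can affect events that the protocol itself classes as serious, and it is cheap to remove.

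**What to change.** - Keep the TEAE definition and tables.
- Add AE and SAE tables by arm for onset from the first dose after randomisation to the End of Study Visit, plus later related SAEs, with a flag for on-treatment or post-treatment onset.
- State for the worst-severity and fatal-event rows of 15.1.1 whether they cover TEAEs or all AEs.
- State in 15.2.2 that the listing covers all collected SAEs, whatever their onset relative to the last dose.
- Note the analysis window in SAP Section 7.

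The cost is SAP wording and slight extra programming on data that the protocol already collects. Event counts may be slightly higher than in the TEAE tables.

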The Investigator is required to grade the severity or toxicity of each AE.

Investigators must assess the severity of AEs per the Qualitative Toxicity Scale, as follows:

Mild: The participant is aware of the event or symptom, but the event or symptom is easily tolerated.

Moderate: The participant experiences sufficient discomfort to interfere with or reduce his or her usual level of activity.

Severe: Significant impairment of functioning: the participant is unable to carry out his or her usual activities.

Investigators must also systematically assess the causal relationship of AEs to study intervention (including any other non-study interventions, radiation therapy, etc.) using the following definitions. Decisive factors for the assessment of causal relationship of an AE to the study intervention include, but may not be limited to, temporal relationship between the AE and the study intervention, known side effects of study intervention, medical history, concomitant medication, course of the underlying disease, and study procedures.

Unrelated: Not reasonably related to the study intervention. AE could not medically (pharmacologically/clinically) be attributed to the study intervention under study in this clinical study protocol. A reasonable alternative explanation must be available.

Related: Reasonably related to the study intervention. AE could medically (pharmacologically/clinically) be attributed to the study intervention under study in this clinical study protocol.

Abnormal Laboratory Findings and Other Abnormal Investigational Findings

Abnormal laboratory findings and other abnormal investigational findings (e.g., on an ECG trace) should not be reported as AEs unless they are associated with clinical signs and symptoms, lead to study intervention discontinuation or are considered otherwise medically important by the Investigator. If a laboratory abnormality fulfills these criteria, the identified medical condition (e.g., anemia or increased alanine aminotransferase [ALT]) must be reported as the AE rather than the abnormal value itself.

Serious Adverse Events

An SAE is any untoward medical occurrence that at any dose:

- Results in death
- Is life-threatening. Life-threatening refers to an event in which the participant is at risk of death at the time of the event, not an event that hypothetically might have caused death if it was more severe.
- Requires inpatient hospitalization or prolongs an existing hospitalization

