## **9 General Specifications for Data Analyses**

### **Study intervention groups**

Study intervention groups are defined and labelled as Crinone® and combination medication (Crinone® plus Duphaston®).

Unless otherwise indicated all analyses will be presented separately for the two study intervention groups.

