**15.1.2 Adverse Events Leading to Study Intervention Discontinuation**

The following overall frequency tables will be prepared for the adverse event actions for the first study intervention by PT and primary SOC in alphabetical order.

- AEs causing discontinuation of at least one study intervention (either Crinone or Duphaston)
- AEs causing discontinuation of Crinone
  - Crinone only related AEs causing discontinuation of Crinone
- AEs causing discontinuation of Duphaston
  - Duphaston only related AEs causing discontinuation of Duphaston

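### SAP 15.1.2 omits discontinuations judged related to both drugs from its related rows, and SAP 15.1 does not limit the missing-is-related rule to drugs received

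*SAP*

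**What the plan says.** SAP 15.1 (Definitions) states that AEs related to study intervention "are those events with relationship missing, unknown or yes". No condition is attached about which drug the subject received.

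SAP 15.1.1 splits related TEAEs into four rows: "Any either trial drug related TEAEs", "Any Crinone only related TEAEs", "Any Duphaston only related TEAEs" and "Any TEAEs related to both drugs". The same split is repeated for serious TEAEs, severity and deaths, so causality has to be held separately for each drug.

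SAP 15.1.2 has three all-cause rows (discontinuation of at least one drug, of Crinone, of Duphaston). Under the Crinone row the only related line is "Crinone only related AEs causing discontinuation of Crinone", with a matching line for Duphaston. It has no line for AEs related to both drugs or to either drug.

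SAP section 9 adds: "Unless otherwise indicated all analyses will be presented separately for the two study intervention groups".

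Protocol Appendix 3 says: "Investigators must also systematically assess the causal relationship of AEs to study intervention". Its scale has two levels, Unrelated and Related, set against the study intervention as a whole. It describes no per-drug field and no not-applicable category.

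**The concern.** Safety of one regimen against the other is a stated secondary objective (Protocol section 3, SAP section 5), so a reader will set the related rows of the two arms side by side. A row restricted to one drug alone means different things in the two arms. With a single assigned drug it can hold every event related to that drug. With two drugs it excludes every event attributed to both. Both products are progestogens given for the same purpose, so attribution to both is foreseeable. In 15.1.2 the exclusion works in one direction and makes the two-drug arm look better.

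The missing-causality rule raises a second question. It is a sensible conservative rule for an assessment that should exist but does not. The SAP does not say what happens to Duphaston causality in a woman who was never given Duphaston.

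**Working it through.** The plan gives no figure to reproduce, because this is a classification rule. The check applies the rule (missing, unknown or yes counts as related) to each drug separately and reads off the resulting row. The last column takes the AE to have stopped Crinone.

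| Arm | Crinone causality | Duphaston causality | 15.1.1 row | In the 15.1.2 Crinone-related row? |
|---|---|---|---|---|
| Combination | yes | no | Crinone only | yes |
| Combination | yes | yes | both | **no** |
| Combination | yes | missing or unknown | both | **no** |
| Crinone | yes | unrelated or not applicable | Crinone only | yes |
| Crinone | no | unrelated or not applicable | not related | no |
| Crinone | yes | blank | both | no |
| Crinone | no | blank | Duphaston only | no |

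**Discontinuation rows.** Let R be the number of combination-arm women with a Crinone-related AE that stops Crinone, one such AE each, and s the share judged related to both drugs. The 15.1.2 row shows R × (1 − s): all of them if s = 0, half if s = 0.5, none if s = 1. The documents give neither R nor s. Under ordinary coding the Crinone-arm row has no such loss. The third line of the table adds a side effect: in the combination arm, a missing Duphaston causality moves a Crinone-related event into the both category and so out of the 15.1.2 related rows. There the conservative rule lowers the count.

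**Missing-causality rule.** The last two lines of the table apply only if the field is blank and the rule is used per drug. In the Crinone arm, *Crinone only* is then always 0, *either drug* equals all TEAEs, and *Duphaston only* plus *both* also equals all TEAEs. The Crinone-arm row in 15.1.2 would be empty as well.

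Illustration: 334 planned participants at 1:1 (Protocol 4.1 and 6.3.1) give 334 / 2 = 167 per arm. The rates are assumptions, with one event per woman: 40% have a TEAE, and 10% of those TEAEs are Crinone-related.

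- Women with a TEAE: 167 × 0.40 = 66.8
- Crinone-related: 66.8 × 0.10 = 6.7
- Remainder: 66.8 − 6.7 = 60.1

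| Crinone-arm row | Duphaston coded unrelated or not applicable | Duphaston left blank |
|---|---|---|
| Either drug | 6.7 | 66.8 |
| Crinone only | 6.7 | 0 |
| Duphaston only | 0 | 60.1 |
| Both | 0 | 6.7 |

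With TEAE rates assumed between 20% and 60% and Crinone-related shares between 5% and 30%, the *either drug* row would show 20% to 60% of women. The correct figure would be 1% (0.20 × 0.05) to 18% (0.60 × 0.30).

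**The case against.** A reader might infer that Duphaston causality is missing by design in the Crinone arm, so that its related rows are wrong as planned. The documents do not support that. The AE eCRF page and its coding are not shown. Appendix 3 requires investigators to assess causality, and an AE in a woman who never took Duphaston can be called Unrelated because it could not be attributed to that drug. The SAP rule is also worded for study intervention as a whole, so applying it per drug is a reading, though a natural one given the per-drug rows. A count of Duphaston-related events in women with no Duphaston record would also be conspicuous in the output.

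A reader might also take the related rows as the main safety summaries. Protocol 9.4.1.3 and 9.4.4 define safety by the incidence and severity of all AEs, with no split by relatedness. The all-cause rows are untouched, and no confirmatory testing is planned.

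For 15.1.2, the defence is that the line is labelled honestly and sits under an all-cause row that keeps every event. In 15.1.1 the *either drug* row is comparable between arms under ordinary coding, and *both* is shown separately.

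Most of this stands, and it limits the second issue to a conditional one. It does not remove the first: 15.1.2 has no *both* or *either* line, so an event related to both drugs appears in no related-discontinuation row. Nor is Unrelated a clean default, because Appendix 3 also asks for a reasonable alternative explanation.

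**Conclusion.** The point holds in two parts, and both are minor.

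- **SAP 15.1.2.** The omission of both-related events from the combination arm's related rows follows from the row definitions alone. Under ordinary coding the Crinone arm has no matching loss, so the related rows are not comparable and understate the combination arm. The loss equals the share attributed to both drugs, which is not known from the documents. In 15.1.1 the weakness is milder: there is no line for all AEs related to one drug, and women counted under *only* and *both* cannot simply be added, because one woman may appear in each.
- **SAP 15.1.** The missing-is-related rule has no limit to drugs received. If the field is blank and the rule is applied per drug, every Crinone-arm TEAE is tabulated as Duphaston-related. If it is coded unrelated or not applicable, nothing is misclassified. The illustrated counts are a conditional worst case on assumed rates.

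The totals for any TEAE, any serious TEAE and all-cause discontinuation are correct in every case.

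**What to change.** 1. In SAP 15.1.2, replace the two single-drug related lines with *Crinone-related, irrespective of Duphaston* and *Duphaston-related, irrespective of Crinone*. Add the same lines in 15.1.1. Show the *only* and *both* splits for the combination arm alone.
2. In SAP 15.1, add: *Missing or unknown causality is counted as related only for a drug the subject received on or before AE onset; for any other drug, causality is set to not applicable.*

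Before finalising the tables, confirm how the AE eCRF records causality for a drug not given. That settles whether the second change alters any output.

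The cost is a few lines of SAP text and a small change in table programming. No new data are needed, since the existing rows already require causality per drug.
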